6. Conduct sensitivity analyses by estimating results with missing baseline data excluded from the analysis (i.e., use case-wise deletion for all cases with missing baseline and outcome data). In an appendix, we will report our benchmark results next to the sensitivity analysis results to verify findings.

d. **Assessment of baseline equivalence:** Baseline equivalence will be reported for all baseline measures of each outcome variable as well as relevant demographic and sexual behavioral measures. We first list and describe the measures we will use to examine the equivalence of our treatment and control group at baseline. After we identify the measures, we provide details on the diagnostic methods that we will use to assess any baseline difference that may exist between the treatment and control groups in the measures outlined below.

Demographic and Sexual Behavior Measures

Baseline equivalence will be assessed for five demographic variables and one baseline measure of sexual behavior (identified below).²⁹ Age is constructed from data reported by agency staff or therapists in the *Recruitment and Eligibility Screening Form*. Race, ethnicity, and education are constructed using participant self-responses to questions in the THS baseline *Participant Questionnaire*. For the race variables, categorical responses to a single question are used to create multiple dichotomous variables. The sexual behavioral variable is constructed from participants' responses to three questions in the baseline *Participant Questionnaire*. We provide details on variable coding below; details on variable construction can be found in Table 2 in the Appendix.

Demographic:

- Age at screening (continuous; range 14-19)³⁰
- Race³¹
- Hispanic/Latino
- Completed high school (0 = has not completed high school; 1= has completed high school)

Sexual Behavior:

- Ever had sex (0=never had vaginal, anal, or oral sex; 1=has had vaginal, anal, and/or oral sex in lifetime);

²⁹ Baseline equivalence will also be reported for gender out of convention. However, gender is a blocking variable used in our randomization process, so the proportions of individuals by gender who are assigned to treatment and control will be balanced by design. Gender at screening is determined using the participant's gender, as reported by agency staff or therapists.

³⁰ Age at screening is determined using the participant's date of birth, as reported by agency staff or therapists.

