We propose to assess baseline equivalence of the treatment and control groups according to a multi-step procedure. Baseline equivalence statistics will be produced for each analytic sample.³² Only participants who provide baseline data to an outcome measure will be included in the analytic sample for that same outcome measure; thus the analytic sample used for each research question may vary slightly because of the exclusion of non-responders. As required by the “Identifying Programs that Impact Teen Pregnancy, Sexually Transmitted Infections, and Associated Sexual Risk Behaviors” review protocol, we will report the adjusted means and p-values of the differences in the baseline variable of interest for the treatment and control groups.³³ We will also report the standardized mean difference of each baseline variable for the treatment and control groups. This last statistic is not required by the review protocol but it is more consistent with the literature on balance statistics.³⁴

To establish baseline equivalence, we propose to generate model-based point estimates of the difference between the treatment and control groups for the identified baseline equivalence variables. We will report the adjusted means and p-values of the differences in the baseline variable of interest for the treatment and control groups. We will then compute the pooled standard deviation of these variables. Finally, we will produce a standardized difference of means by dividing the first term by the second.³⁵

step 1. First, we generate a model-based estimate of the difference between treatment and comparison groups on the pre-intervention measures identified above. Separate models will be run for each of the variables. The empirical model will be estimated with OLS (using Stata). If the measure is dichotomous, we propose to use a linear probability model to estimate the predicted probability of group membership. The model is a reduced-form variation of the model that we use to estimate program impact (as detailed in the *Model specification and covariates* section, below).³⁶

$$Y_{baseline} = \beta_0 + \beta_1 T + \sum (\beta_p X_p) + \varepsilon$$

where:

³² Due to item missing outcome data, we expect there may be slight differences in analytic samples for each research question.

³³ Goesling, B., & Trenholm, C. (2016). Identifying Programs that Impact Teen Pregnancy, Sexually Transmitted Infections, and Associated Sexual Risk Behaviors. Mathematica Policy Research.

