³⁴ The literature on balance statistics argues that significance testing is inappropriate for this diagnostic task (Austin, 2007; Imai et al., 2008; Austin, 2009; Stuart, 2010). Hypothesis tests can be misleading diagnostic measures of baseline equivalence because they conflate balance with statistical power.

³⁵ Note that we will produce diagnostic estimates of baseline equivalence on the exact same samples of observations that we will use in our primary analysis. In other words, we will apply the missing data approach outlined in section 4cv prior to producing estimates of baseline equivalency on the pre-intervention measures.

³⁶ It is a reduced- form because individual-level, demographic covariates are omitted. It is a variation because the dependent variable is the baseline equivalence variable, not the outcome measure.

$Y_{baseline}$ – is the baseline measure of the variable that we use to establish baseline equivalency (identified in the Appendix – Table 2 above). This variable is included as a covariate in the analytic model (see Table 2 in the Appendix for details on variable coding). Separate models will be estimated for each baseline equivalency measure specified above.

T – A dummy treatment indicator variable whose value equals 1 if the participant is randomized into the treatment group and zero otherwise.

X – A p vector of blocking variables (i.e., subgroups within which random assignment occurred) to account for the variation in the baseline variables associated with these groups. Blocking variables include:

- a) State – An $n-1$ vector of state indicator dummy variables that are coded one if the intervention was delivered at state n and coded zero otherwise.
- b) Female – A dummy variable that is coded 1 if the participant self-reported being female at screening and coded 0 otherwise.

β_0 – The intercept term, which represents the adjusted mean value of the baseline equivalency measure for participants in the control sample, with all other variables in the model held constant at zero.

β_1 – This represents the adjusted (but not standardized) mean difference in the baseline equivalency variable between treatment and control participants.

ε – The residual or random variation that remains for each observation after the structural components of the model are estimated. It is the difference between the observed and the predicted values at the individual level.

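### The step 1 balance model has Female on both sides for the gender row, so that row's adjusted difference, adjusted means and p-value cannot show gender imbalance after attrition

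*Combined protocol and SAP*

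**What the plan says.** Section 4)d announces five demographic variables for the equivalence assessment but bullets four: age, race, Hispanic/Latino and high school completion. Footnote 29 supplies the fifth: "Baseline equivalence will also be reported for gender out of convention". It explains that gender is a blocking variable, "so the proportions of individuals by gender who are assigned to treatment and control will be balanced by design".

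Under Balance Assessment Methods, step 1 gives one model form, Y_baseline on T plus a vector X of blocking variables, and says: "Separate models will be run for each of the variables". The definition of Y_baseline repeats this: "Separate models will be estimated for each baseline equivalency measure specified above". For binary variables, "If the measure is dichotomous, we propose to use a linear probability model". X holds the state dummies and Female: "A dummy variable that is coded 1 if the participant self-reported being female at screening and coded 0 otherwise". No exception is made for gender.

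Step 2 reports adjusted means and p-values. Step 4 gives the Cox index as the effect size for dichotomous variables, computed from p_t and p_c. It does not say whether these are observed or model-adjusted.

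Footnote 35 places the whole assessment "on the exact same samples of observations that we will use in our primary analysis", that is, after cases without nine-month outcome data have been deleted (section 4)c v, step 4).

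**The concern.** A variable regressed on itself is fitted perfectly, and nothing is left for treatment to explain. The gender row would then report no adjusted difference however the arms differ.

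Blocking balances gender among those randomised. The balance table describes those who remain at nine months, and boys or girls could be lost at different rates in the two arms. The attrition formulas in section 4)f ii are overall and by arm, not by gender. The gender row is therefore the place in the plan where gender-differential loss would be expected to appear. At stake is whether that row can do its job.

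**Working it through.** The plan states no figure on this point, so there is none to reproduce.

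**Algebra.** Put gender into step 1:

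Female = b0 + b1·T + Σ(b_s·State_s) + b_F·Female + e

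Least squares has the exact solution b_F = 1, all other coefficients 0 and all residuals 0. Hence:

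- The adjusted difference b1 is 0.
- The adjusted means are equal in the two arms at any fixed covariate values.
- The p-value is formed from 0/0, so whatever the software prints is rounding noise.

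**Illustration: inputs.**

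- From the documents: 400 enrolled (Study Changes Timeline, November 2018), 1:1 allocation blocked by state and gender, five states.
- Assumed, because the documents do not give them: equal-sized states, 50% to 80% female at enrolment, and the retention rates below.

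**One case by hand (50% female).** Each state × gender × arm cell holds 400 / 5 × 0.5 / 2 = 20. Assume retention of 85% for control males, 75% for control females, 60% for treatment males and 90% for treatment females.

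- Control, per state: 17 males and 15 females, so the female share is 15/32 = 46.9%.
- Treatment, per state: 12 males and 18 females, so the female share is 18/30 = 60.0%.
- Raw difference: 60.0 − 46.9 = 13.1 points, with 5 × (32 + 30) = 310 analysed.
- Step 1 as written: b1 = 0 to machine precision, b_F = 1.0000, residual sum of squares about 0.
- Step 1 with T and State only: b1 = 0.131, SE 0.057, p = 0.021.
- Cox index from observed shares: [ln(18/12) − ln(15/17)] / 1.65 = (0.405 + 0.125) / 1.65 = 0.32.

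**Range over 50% to 80% female at enrolment** (cell counts rounded to whole participants):

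| Assumed retention, males/females | Step 1 as written, b1 | T + State only, b1 | p | Observed Cox index |
|---|---|---|---|---|
| Both arms 80/80 | 0 | 0 | 1.0 | 0 |
| Control 80/80, treatment 65/85 | 0 | 0.031 to 0.073 | 0.19 to 0.46 | 0.13 to 0.19 |
| Control 85/75, treatment 60/90 | 0 | 0.079 to 0.131 | 0.021 to 0.070 | 0.32 to 0.33 |

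In all 12 scenarios the model as written gave |b1| below 2e-15. Dropping Female from X for this row recovers the imbalance where there is one and returns zero where there is none.

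**Cox index under the two readings.** With observed proportions it takes the values in the last column. With adjusted means from the step 1 model the two inputs are equal: the index is 0 if Female is held at its mean, and undefined (logit of 0) if Female is held at zero, as the plan's definition of the intercept has it.

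**Field identity.** Footnote 29 takes gender from agency staff or therapists, whereas step 1 describes Female as self-reported. If these are separate fields that mostly agree, b1 measures only how their disagreement differs between arms. It is then near zero, not exactly zero, and still says nothing about gender balance.

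**The case against.** A reader might infer that the balance table would show perfect gender equality whatever happened. The documents do not support that. The plan's effect size for a dichotomous variable is the Cox index, and its p_t and p_c are described as probabilities within each group, with no mention of adjustment. Read plainly, these are observed shares, and the index would show the imbalance. The plan also says that standardised differences fit the balance literature better than p-values (section 4)d and footnote 34), so the diagnostic it favours may be intact. This stands, and it limits the point to the adjusted difference, adjusted means and p-value. It does not remove the point, because step 2 commits to reporting those statistics. On that reading, an adjusted difference of zero could sit beside a Cox index of 0.32 in the same row.

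A reader might also take footnote 29 to claim that gender cannot become unbalanced. It does not: it speaks of those assigned, and for them it is right.

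Routing gender through step 1 is an inference, since no gender model is written out. It is a reasonable one: the count of five variables needs gender, the model is to be run for each variable, and no other method is offered.

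Finally, the practical effect is small. The primary model already adjusts for Female (section 4)f i), section 4)d ties no decision rule to the balance results, and an analyst would probably notice a perfect fit. All of that stands.

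**Conclusion.** The point holds as a narrow specification error. Applied as written, step 1 gives a zero or near-zero adjusted difference, equal adjusted means and a meaningless p-value for gender, whatever attrition has done to the analytic sample. This follows from the algebra and needs no assumption about retention. It rests only on gender being put through step 1, which the text implies but does not spell out.

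How much imbalance would be hidden cannot be derived from the documents. Under the assumed unequal-retention patterns it is about 3 to 13 percentage points. Whether the Cox index also fails depends on the unstated choice between observed and adjusted proportions. The primary effect estimate is unaffected.

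**What to change.** In section 4)d, step 1, add that when gender is the balance variable, X contains the state dummies only. In step 4, add that the Cox index for gender is computed from the observed proportions in the analytic sample. It would also help to say which gender field is used, since footnote 29 and step 1 name different sources. Footnote 29's remark on balance by design is correct for assignment and can stay.

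The cost is two or three sentences of wording. Data collection, the design and the primary analysis do not change.

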We operationalize times having sex without a condom as a risk outcome; that is, we measure the frequency with which participants engage in the risk behavior of having sex without a condom, rather than the frequency with which they engage in the safe sex practice of using condoms.

Constructing the variable in this way allows us to examine the self-reported sexual behaviors of the full analytic sample of participants, regardless as to whether or not they are sexually active.

Specifically, times having sex without a condom is constructed as a continuous variable – the number of times in the past three months a participant *does not* use condoms while engaging in any type of sex.¹³ Data used to assess the impact of the treatment (*PS-R*) on condom use are obtained from the following three items on the *Participant Questionnaire*, which is administered to both the treatment and control groups at baseline and nine months post-intervention.

- *In the past three months, how many times have you had vaginal sex without using a condom?*
- *In the past three months, how many times have you had oral sex without using a condom?*
- *In the past three months, how many times have you had anal sex without using a condom?*

Persons who indicate that they have not ever had a particular type of sex (vaginal, oral, or anal) or have not had that type of sex in the past three months are coded as having that type of sex without a condom zero times.¹⁴ The final outcome measure is calculated by summing individuals' responses to these three items (the number of times they report they did not use condoms during vaginal, oral, and anal sex).

PS-R will be considered to have a positive impact on times having sex without a condom if the number of times having sex without condoms reported by participants assigned to *PS-R* at the nine-month follow-up is smaller than the times reported by control participants and the difference between groups is statically significant.

Number of Sexual Partners

Number of sexual partners is constructed as a continuous variable – the number of sexual partners the participant reports that they have had in the past three months. Data used to assess the impact of the treatment (*PS-R*) on number of sexual partners are obtained from the following two items on the *Participant Questionnaire*, which is administered to both the treatment and control groups at baseline and nine months post-intervention period.

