- Second, we create an outlier indicator variable, where observations deemed severe outliers are coded as 1, all others are coded as 0.

Our benchmark analytic approach is to include data flagged as outliers in analysis, because we do not know for certain whether the values are true or invalid. However, we also run sensitivity analyses that exclude these data and report substantive differences in the results section of the report.

iv. **Identify and flag inconsistencies in reporting of sexual behaviors:** The fourth step in the data review process is to inspect the data and identify inconsistencies in sexual behavior outcome data. With repeated measures of sexual behaviors, two primary types of inconsistencies may occur – internal inconsistencies and over-time inconsistencies.²⁴ Internal inconsistencies refer to discrepancies in responses (to related questions) in the same survey administration. For instance, a respondent might say that they have not had sex in the past three months, but then indicates that they used condoms three of the times they had sex in the past three months. Over-time inconsistencies refer to instances in which lifetime reported behaviors decline or are completely recanted over time. For example, at baseline a respondent might say that they have had vaginal sex in their life, but on a subsequent administration of the survey say that they have never had vaginal sex.

In order to minimize internal inconsistencies in our primary outcomes, we built skip patterns into the online questionnaire – if participants indicate they have not had a particular type of sex they are skipped out of more specific questions related to that type of sex; and if they state they have never had sexual contact, they are then skipped out of questions asking about how many sexual partners they have had over certain periods of time. In addition, participants are precluded from indicating they had a particular type of sex without a condom more times than they said they had that type of sex. Because of this, no internal inconsistencies can exist in our primary outcome measures.²⁵

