f. **Analytic approach for primary research questions:** As detailed in our primary research questions, this study investigates whether offering *PS-R* to participants impacts their reported number of times having sex without condoms and number of sexual partners. We do this within the intent to treat (ITT) framework, which does not measure the effect of the participant's exposure to the treatment itself but rather the effect of the offer of the treatment relative to the offer of receiving the control condition. This framework maintains the integrity of the experimental structure by including all participants who were randomized (except those who attrite) in the analytic sample, thereby maintaining an exogenous assignment of participants to experimental condition. Bias can be insinuated, however, through self-selection if any participant who is randomized fails to provide outcome data.

i. **Model specification and covariates:** The primary research questions under investigation in this study are whether offering *PS-R* to participants impacts their: (1) reported times having sex without condoms, and (2) reported number of sexual partners (see Table 1 in Appendix for variable constructions). We propose to estimate these impacts using a regression that will model intervention effects as a function of assignment to *PS-R* (i.e., Treatment), relevant baseline covariates, a baseline measure of the outcome variable, and gender and state-level (blocking) indicators (see Table 2 in Appendix for variable constructions). Although a straight difference-of-means approach should provide unbiased estimates of the effect of the treatment, we propose a model-based approach because it will increase the precision of those estimates.³⁹ The empirical model will be estimated with an OLS regression (using Stata).⁴⁰ We present the empirical model here:

$$Y_{Post} = \beta_0 + \beta_1 T + \beta_2 Y_{Pre} + \sum (\beta_P X_P) + \varepsilon$$

Where:

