β_1 – This is the parameter estimate of substantive interest. β_1 represents, depending on the outcome measure of interest in the analysis, either: 1) the adjusted mean difference in treatment and control participants' self-reported times having sex without condoms in the past three months at the nine-month follow-up; or 2) the adjusted mean difference in treatment and control participants' self-reported number of sexual partners in the past three months at the nine-month follow-up.

ε – The error term or unexplained individual-level variance that remains for each observation after the structural components of the model are estimated. It is the difference between the observed and the predicted values at the individual level.

We will report model-estimated effects and the results of significance tests in the findings section of the final impact report. Statistical significance will be based on test statistics produced by Stata for the coefficient β_1 using a two-tailed test, with $p < .05$.

- ii.* **Sample attrition:** Overall and differential attrition will be calculated using the full sample of participants enrolled in the study. This will be determined using data within the *Participant Database*. We will calculate overall attrition using the following formula:

$$Attrition_{participant} = 1 - \left(\frac{Assessed_{participant}}{Base_{participant}} \right)$$

where:

$Attrition_{participant}$ - the proportion of participants enrolled in the study who did not complete a 9-month follow-up questionnaire
 $Base_{participant}$ - the number of participants enrolled into the study
 $Assessed_{participant}$ - the number of participants who completed a 9-month follow-up questionnaire

Differential attrition will be calculated using the following formulas:

$$Attrition_{participant} C = 1 - \left(\frac{Assessed_{participant} C}{Base_{participant} C} \right)$$

$$Attrition_{participant} T = 1 - \left(\frac{Assessed_{participant} T}{Base_{participant} T} \right)$$

$$Differential\ Attrition_{t-c} = abs(Attrition_{participant} T - Attrition_{participant} C)$$

Where:

$Differential\ Attrition_{t-c}$ - the absolute difference between the proportion of treatment group participants who did not complete a 9-month follow-up questionnaire and the proportion of control group participants who did not complete a 9-month follow-up questionnaire

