 $Attrition_{participant} C$ - the proportion of participants enrolled in the study and randomly assigned to the control group who did not complete a 9-month follow-up questionnaire

$Base_{participant} C$ - the number of participants enrolled into the study and randomly assigned to the control group
 $Assessed_{participant} C$ - the number of participants randomly assigned to the control group who completed a 9-month follow-up questionnaire

$Attrition_{participant} T$ - the proportion of participants enrolled in the study and randomly assigned to the treatment group who did not complete a 9-month follow-up questionnaire
 $Base_{participant} T$ - the number of participants enrolled into the study and randomly assigned to the treatment group
 $Assessed_{participant} T$ - the number of participants randomly assigned to the treatment group who completed a 9-month follow-up questionnaire

Overall and differential attrition will be reported in the findings section of our final impact report.

iii. **Adjustments for multiple comparisons:** Following guidance provided under the grant for our impact analysis plan⁴¹, we will adjust for multiple comparisons in all of our primary

⁴¹ During the January 8, 2019 OAH TPP Tier 2b Group Call on Impact Analysis Plans, the presenters noted that multiple comparison adjustment is required for all model-generated effect estimates of primary outcome measures.

outcome s analyses, regardless of outcome domains. We propose to use the Benjamini-Hochberg method.⁴² This method controls for the false discovery rate (FDR), which is the expected value of the number of false positive tests divided by the total number of significant tests within a family of tests. The following procedures will be used to implement this adjustment:

1. The p-values generated by our models of the effect of the intervention on our three primary outcome measures will be ranked from smallest to largest, indexed by i (where $i = 1$ for the smallest p-value and $i = k$ for the largest p-value).

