5. **Condensed data collection windows.** Our benchmark approach is to include follow-up data from all participants who completed a questionnaire during their open data collection window, regardless of the time point in that window when it was completed. Data collection windows are broad to minimize attrition from the analytic sample. To examine whether or not this influences our results – and, in particular, whether or not study participants who respond later report different outcomes from those who respond earlier – we will conduct an analysis that examines the difference, if any, in response time between treatment and control participants and compares impact estimates for analytic samples without late responders. Late responders will be defined as those participants who complete their nine-month questionnaire more than one month after the initiation of the nine-month data collection window.
6. **Using alternate model specification.** Our benchmark approach is to use OLS regression to estimate the effects of the intervention on each of our primary outcomes of interest. This approach is deemed appropriate even in the instance the dependent variable is not normally distributed – as may be the case with our outcomes – so long as the sample size is sufficiently large.⁴³ In the instance our analytic sample size does not reach 500 participants (the threshold at which we consider a sample large), we propose to conduct diagnostic tests to identify an appropriate alternative estimation approach (e.g., transformation of the dependent variable, Bayesian approach, non-parametric model) that will be used to conduct sensitivity analyses to test the robustness of our results.

5. **Additional planned analyses:** We intend to investigate the following exploratory research questions in addition to the primary research questions described above.

Antecedents of Sexual Behavior

- a. What are the short-term (post-program) and long-term (nine-month follow-up) impacts of the offer to participate in *PS-R* (treatment) relative to the offer to participate in *TPG* (comparison) on the following antecedents of participants' sexual behavior:
 - i. Perception of risk and severity for pregnancy and HIV/STIs

⁴³ Lumley, T., Diehr, P., Emerson, S., Chen, L. (2002). The Importance of the Normality Assumption in Large Public Health Datasets. *Annual Review of Public Health*. 23:151–69
DOI: 10.1146/annurev.publhealth.23.100901.140546

- ii. Intention to have sex

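### No variance estimator is named for the primary OLS tests; the ordinary SE fails at any sample size if the arms differ in both residual variance and analysed size

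*Combined protocol and SAP*

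**What the plan says.** **Model and test (4)f.i).** "The empirical model will be estimated with an OLS regression (using Stata"), on the raw outcome, with treatment, the baseline outcome, covariates and blocking indicators. On inference: "Statistical significance will be based on test statistics produced by Stata for the coefficient" β1, two-sided at 5%. The resulting p-values go into a multiplicity step (4)f.iii): "We propose to use the Benjamini-Hochberg method". No variance estimator is named anywhere.

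**Outcomes (4)a, 4)c.iii).** Sex without a condom is a total of three self-reported counts: "The final outcome measure is calculated by summing individuals' responses to these three items". For the other outcome, "Number of sexual partners is constructed as a continuous variable", although it too is a count. Youth with no sexual activity are scored zero on both. The component items have no upper limit, and extreme values stay in: "Our benchmark analytic approach is to include data flagged as outliers in analysis".

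**Analysed sample.** Allocation is 1:1. Anticipated enrollment was cut from 600 to 400 (Study Changes Timeline, November 2018). Participants without nine-month outcomes are deleted (4)c.v, step 4). Attrition by arm will be reported (4)f.ii), but no rate is anticipated. Sensitivity analyses drop phone interviews (3)d), outliers and late responders.

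**Defence of OLS (sensitivity analyses, item 6).** "This approach is deemed appropriate even in the instance the dependent variable is not normally distributed", provided the sample is large. The plan sets large at 500 analysed. Below that, an alternative estimation approach is sought, for sensitivity analysis only.

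**The concern.** Default OLS output assumes one residual variance for everyone. In counts with many zeros and a long right tail, variance usually rises with the mean, so a treatment that lowers the mean will usually lower the variance in its arm. The ordinary SE for β1 pools the two variances with weights set by arm size, whereas the true SE divides each arm's variance by its own n. The two agree if the arms are equal in size or equal in variance. Otherwise they differ, and more data does not close the gap, because the fault is in what the formula estimates. A large-sample argument about non-normality does not reach it.

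At stake are the SEs, p-values and power for the two primary comparisons when PS-R has an effect, and the test itself if PS-R alters spread but not the mean. The direction of the error would depend on which arm loses more youth, which the sponsor cannot control.

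**Working it through.** The plan gives no power calculation, SD, effect size or attrition rate, so there is no figure of its own to reproduce.

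**Inputs from the documents:** 1:1 allocation, 400 enrolled (200 per arm), two-sided 5%, case deletion of missing outcomes.
**Assumed:** attrition by arm, the variance ratio V = Vt/Vc, and the simulated count distributions. If SD is proportional to the mean, a 30% lower mean gives V = 0.7² = 0.49 and a 50% lower mean gives V = 0.5² = 0.25.

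**1. Formulae** (t = PS-R, c = control)
- True SE = √(Vt/nt + Vc/nc)
- Ordinary SE = √[Sp²(1/nt + 1/nc)], with Sp² = [(nt−1)Vt + (nc−1)Vc]/(nt+nc−2)
- R = true SE / ordinary SE; actual two-sided error = 2[1 − Φ(1.960/R)]

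**2. One case in full:** 180 PS-R, 140 control, Vc = 1, V = 0.49.
- True variance: 0.49/180 + 1/140 = 0.00272 + 0.00714 = 0.00987
- Sp² = (179×0.49 + 139)/318 = 0.7129; ordinary variance: 0.7129 × (1/180 + 1/140) = 0.7129 × 0.01270 = 0.00905
- R = √(0.00987/0.00905) = 1.044; error = 2[1 − Φ(1.960/1.044)] = 6.0%

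**3. Range**

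| Analysed PS-R/control | Attrition PS-R/control | V | R | Actual error |
|---|---|---|---|---|
| 160/160 | 20%/20% | 1 to 0.25 | 1.000 | 5.0% |
| 180/140 | 10%/30% | 1 | 1.000 | 5.0% |
| 160/150 | 20%/25% | 0.49 | 1.011 | 5.3% |
| 160/150 | 20%/25% | 0.25 | 1.020 | 5.5% |
| 160/140 | 20%/30% | 0.49 | 1.023 | 5.5% |
| 180/140 | 10%/30% | 0.49 | 1.044 | 6.0% |
| 180/140 | 10%/30% | 0.25 | 1.078 | 6.9% |
| 140/160 | 30%/20% | 0.49 | 0.977 | 4.5% |
| 140/180 | 30%/10% | 0.25 | 0.927 | 3.5% |

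The first two rows show that neither condition alone matters. The last two show the error reversing.

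**4. Simulation of a condom-type count** (45% structural zeros, negative binomial k = 0.5, control mean 8, 320 analysed, 6,000 trials per scenario). Non-coverage is the share of nominal 95% intervals that miss the true difference; its simulation error is about √(0.05×0.95/6000) = 0.3 points.

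| Arms | Reduction | Ordinary SE | Non-coverage, ordinary v HC3 |
|---|---|---|---|
| 160/160 | – | no material error | 4.7% v 4.6% |
| 180/140 | 30% | 4% too small | 6.0% v 5.2% |
| 180/140 | 50% | 9% too small | 7.5% v 5.6% |
| 140/180 | 30% | 3% too large | 4.4% v 5.0% |
| 140/180 | 50% | 7% too large | 3.9% v 5.2% |

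A repeat with 8,000 trials gave 5.6% v 4.8% and 7.9% v 6.0% for the two 180/140 rows. At a 5-point gap (165/155) with a 30% reduction, two runs gave 5.8% v 5.5% and 5.2% v 5.0%. With identical distributions at 180/140, the ordinary test rejected 4.8% to 5.0% of the time.

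**5. Does a larger sample cure it?** A second simulation (control mean 6, adjusted for baseline count and sex, 50% lower mean) used HC2, a close relative of HC3:
- 180/140: empirical SD 1.538, ordinary SE 1.423, HC2 1.530; non-coverage 8.4% v 7.4%.
- 1800/1400: empirical SD 0.492, ordinary SE 0.451 (1 − 0.451/0.492 = 8% too small), HC2 0.486; non-coverage 7.1% v 5.6%.

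The ordinary SE stays about 8% short with ten times the sample. The robust SE is close to right at both sizes. What remains at 180/140 is skewness: equal arms of 160 gave 7.0% with either SE.

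**6. Same mean, different spread** (second simulation, dispersion parameter 0.6 v 0.3). At 180/140 the ordinary SE was 1.609 against an empirical SD of 1.676 (4% too small), with error 5.7% v 5.5% under HC2. At 140/180 the error was 4.5% for the ordinary SE.

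**7. Partner-type count** (means 1 v 0.7, 30% structural zeros, k = 2). Ordinary non-coverage was 5.6% at 180/140 and 5.2% at 165/155.

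**The case against.** **The primary test is not shown to be invalid.** This stands. A reader might infer an inflated false-positive rate, but when PS-R leaves the outcome distribution unchanged the test holds 5% even with unequal arms. The plan does not mention confidence intervals either, so non-coverage here measures SE accuracy, not a promised output.

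**Unequal arms alone do no harm.** This stands too. A reader might infer that any imbalance in analysed numbers spoils the SE. It does not, because residual variances must also differ by arm. Variance that changes only with baseline covariates does not break the SE, since treatment is randomised independently of them.

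**The larger figures need an extreme gap.** 180/140 means 10% v 30% attrition, and footnote 39 argues on the assumption that attrition and its difference between arms are low. At a 5-point gap the SE error is about 1%.

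**The balance models.** A reader might extend the point to the linear probability models in 4)d. The documents do not support that. Those outcomes are measured at baseline, so PS-R cannot have changed their variance; only selective attrition could. Footnote 34 already discounts significance tests for balance. With an assumed 60% prevalence in both arms at 180/140, rejection was 4.8% ordinary v 4.7% HC3.

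**Item 6 already provides an alternative.** With 400 expected and a threshold of 500, it should be triggered. But it yields a sensitivity analysis only, so the benchmark SE stays as it was.

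**The ordinary SE is an inference.** True: the estimator is simply unnamed. That leaves a choice open until after the data are seen, which one sentence would close.

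**Conclusion.** The point holds in a limited form. The plan names no variance estimator for β1, its outcomes make equal variance doubtful if PS-R works, and its stated defence does not address this. If residual variance and analysed size both differ between arms, the ordinary SE is wrong at any n, in a direction set by which arm is larger.

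The error is modest: about 1% of the SE at a 5-point attrition gap, and about 4% to 9% at a 20-point gap. At that larger gap non-coverage is about 6% to 8% when the SE is too small, and about 4% when it is too large. The partner count appears less affected than the condom count. All these sizes rest on assumed distributions, effects and attrition; the existence and direction of the error do not. The harm is to SEs, p-values and power when there is an effect, or to the test if spread changes without the mean. The correction is worth making because it is nearly free, not because the primary conclusion is in serious doubt.

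**What to change.** Add one sentence to 4)f.i: SEs and p-values for β1 use heteroskedasticity-consistent (HC3) variance in the benchmark and in every OLS sensitivity impact model, by adding `vce(hc3)` to the regress command. The HC3 p-values then enter the Benjamini-Hochberg step. In sensitivity item 6, say that the large-sample argument concerns non-normality and that the robust variance deals with unequal variance. The balance models in 4)d need no change on this account.

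**Cost:** one Stata option. Coefficients, estimand and data collection are unchanged, and with equal arms the results barely move. With unequal arms power shifts by a few points: in the simulated 30% reduction, from 31.5% to 27.4% at 180/140 and from 27.3% to 31.4% at 140/180. The loss at 180/140 comes from replacing an SE that was too small. HC3 does not remove the skewness error at around 320 analysed, so the alternative-model analysis in item 6 is still needed.
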